4. SAMPLE SIZE

This is a PMCF study. The primary endpoint is a customized symptom and quality of life questionnaire. An arbitrary cohort of 200 children has been chosen. A cohort of 100 children in the Healsea® Babykids arm and 100 children in the Placebo arm is anticipated to allow to demonstrate the interest of using Healsea® Babykids in the acute infectious rhinitis. Indeed, 100 patients by arm are enough to detect a Cohen's effect size of 0.4 with a power of 80% and a type I error of 5%. Cohen's effect size is defined as the standardized difference between area under the curve (AUC) in groups. According to Cohen's methodology, 0.4 is an intermediate size between a small effect (0.2) and a medium effect (0.5) and is coherent with the expected result. The Placebo arm will be used as the reference group.

Study Number: LPH-2202

BASICC

The recruitment will be performed using a 1:1 randomization ratio.

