6. STATISTICAL METHODS

6.1. Data processing

The analyses will be computed with SAS Version 9.4 TS Level 1M6 Copyright (c) 2016 by SAS Institute Inc., Cary, NC, USA.

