6.3. Statistical/Analytical issues

6.3.1. Significance level

All statistical analyses will be performed at the 0.05 global significance level (type I error rate), using two-sided tests.

The statistical results will only allow to conclude on the primary efficacy criterion. All other statistical results have to be considered within a descriptive perspective and not as inferential issues. No adjustment for Type I error will be done. P-values of statistical tests on secondary criteria will be provided for information only.

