10.2. Analysis of the secondary efficacy criteria

The analysis of the secondary efficacy criteria will involve multivariate analysis.

The selection of variables in multivariate analysis will be performed using a 0.20 significance level and a stepwise method. Covariates considered as potential confounding factors to be initially tested with the treatment in the multivariate models are:

- Body temperature at baseline (°C);
- Scores to each of the items 2 to 7 of the ARSSO at baseline.

All multivariate analyses below will follow this logic.

10.2.1. Modelling of AUC on global score by multivariate ANCOVA

A multivariate ANCOVA model of the AUC on global score of ARSSQ during the first eleven days of the study will be performed.

Patients will be analysed on the FAS and the PP Set.

AXIODIS CRO 17/47

10.2.2. Durations of cold symptoms and of impacts on Quality-of-Life

Hereinafter, the "recovery date" is the first day of the two first consecutive days the patient gave a negative answer to the question 1 ("not sick") without giving a positive answer to the same question (other than "not sick") later. Otherwise, there is no "recovery date" for the patient.

The scores of cold symptoms and of impact on Quality-of-Life (QoL) will be computed at each time-point the patient completed the questionnaire (see §6.4.6), using the following formulae:

At each time point t: ARSSQ_{SYMP}(t) =
$$\sum_{j \text{ in } \{2; ...; 7\}} ARSSQ_{j}(t)$$

ARSSQ_{QOL}(t) = $\sum_{j \text{ in } \{8; ...; 10\}} ARSSQ_{j}(t)$

• The duration of common cold is defined as the duration between the reference start date and the recovery date.

Common cold's duration (days) = Recovery date - Reference start date

The origin date will be the reference start date.

The considered event is the end of common cold, i.e. the recovery of the patient. The event date will be the last day before the recovery date.

Patients without recovery date will be censored at D18 or at the end of the study, and the censoring date will be the date of D18 or the reference end date, whichever occurs first.

• The duration of the cold symptoms is defined as the duration between first symptomatic day and last symptomatic day.

Cold symptom's duration (days) = Last symptomatic day - first symptomatic day + 1

The first symptomatic day is the first day the patient had a non-zero and non-missing score of cold symptoms. It will be the origin date.

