Since the computed duration in the three cases is a recovery time and not a survival time, unlike the usual case of application of Cox survival regression, the provided hazard ratios will measure the likeliness of the recovery.

Consequently, and particularly for the treatment (with Placebo as reference), a hazard ratio greater than 1 will have to be considered under a positive aspect, because it will significate that the recovery is more likely under Healsea[®] Babykids treatment than under Placebo. On the contrary, a hazard ratio lower than 1 will have to be considered under a negative aspect.

For the three durations, a forest plot of the hazard ratios and their 95% CIs from the final multivariate Cox survival regression model will be provided.

AXIODIS CRO 19/47

In addition, for the three durations, a Kaplan-Meier graph will be provided. Survival curves will be drawn by treatment group. Number of sick / symptomatic / impacted patients, number of events (recoveries) and number of censors in each arm will be displayed on the same graph, as well as the log-rank p-value.

For the same reason as above and unlike the usual case of application of Kaplan-Meier graph, if the log-rank p-value is under 5%, a survival curve for Healsea[®] Babykids group under the curve for Placebo group will have to be considered under a positive aspect, and the contrary under a negative aspect.

Patients will be analysed on the FAS.

AXIODIS CRO 20/47

Statistical Analysis Plan

10.2.3. Use and number of days of use of conventional common cold medications

A multivariate logistic regression model will be used to analyse use (yes/no) of conventional common cold medications (overall and by therapeutic class: antibiotics, antipyretics, mucolytics, decongestants, antitussives, systemic and topical corticosteroids).

BASICC

A multivariate Poisson regression model will be used to analyse the number of days of use of conventional common cold medications (overall and by therapeutic class).

The number of days of use of these medications is defined as follows:

- A day is counted when the patient used at least one of these medications this day;
- Each day is counted once, whatever the number of these medications used this day;
- The total number is the sum of all distinct days of use of these medications, from D1 to D18.

Patients will be analysed on the FAS.

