F_14_2_2_2_3_2_kmqol_fas.rtf	Figure	14.2.2.3.2	Kaplan-Meier graph for the duration of impact on Quality-of-Life by treatment group – Full Analysis Set	F4
T_14_2_2_3_1_cccmed_fas.rtf	Table	14.2.2.3.1	Impact of the treatment on the intake of conventional common cold medications – Full Analysis Set	T16
T 14 2 2 3 2 antibio fas.rtf	Table	14.2.2.3.2	Impact of the treatment on the intake of antibiotics – Full Analysis Set	T16
T_14_2_2_3_3_antipyr_fas.rtf	Table	14.2.2.3.3	Impact of the treatment on the intake of antipyretics – Full Analysis Set	T16
T_14_2_2_3_4_mucol_fas.rtf	Table	14.2.2.3.4	Impact of the treatment on the intake of mucolytics – Full Analysis Set	T16
T 14 2 2 3 5 decong fas.rtf	Table	14.2.2.3.5	Impact of the treatment on the intake of decongestants – Full Analysis Set	T16
T_14_2_2_3_6_antitus_fas.rtf	Table	14.2.2.3.6	Impact of the treatment on the intake of antitussives – Full Analysis Set	T16
T_14_2_2_3_7_cortico_fas.rtf	Table	14.2.2.3.7	Impact of the treatment on the intake of systemic and topical corticosteroids – Full Analysis Set	T16
T_14_2_3_cm_fas.rtf	Table	14.2.3	Concomitant treatments – Full Analysis Set	T5
T 14 2 4 1 1 1 ae saf.rtf	Table	14.2.4.1.1.1	Summary of non-related adverse events – Safety Set	T17
T 14 2 4 1 1 2 ae fas.rtf	Table	14.2.4.1.1.2	Summary of non-related adverse events – Full Analysis Set	T17

AXIODIS CRO 28/47

Final version – August 09th, 2023

File (BASICC)	Type	Number	Title	Mock
T_14_2_4_1_2_1_trtae_saf.rtf	Table	14.2.4.1.2.1	Non-related treatment-emergent adverse events by System Organ Class and Preferred Term – Safety Set	T18
T_14_2_4_1_2_2_trtae_fas.rtf	Table	14.2.4.1.2.2	Non-related treatment-emergent adverse events by System Organ Class and Preferred Term – Full Analysis Set	T18
L_14_2_4_2_1_1_sae_saf.rtf	Listing	14.2.4.2.1.1	Serious non-related adverse events – Safety Set	L3
L_14_2_4_2_1_2_sae_fas.rtf	Listing	14.2.4.2.1.2	Serious non-related adverse events – Full Analysis Set	L3
L_14_2_4_2_2_1_aedisct_saf.rtf	Listing	14.2.4.2.2.1	Non-related adverse events leading to definitive discontinuation of the trial device – Safety Set	L3
L_14_2_4_2_2_2_aedisct_fas.rtf	Listing	14.2.4.2.2.2	Non-related adverse events leading to definitive discontinuation of the trial device – Full Analysis Set	L3
L_14_2_4_2_3_1_aediscs_saf.rtf	Listing	14.2.4.2.3.1	Non-related adverse events leading to definitive discontinuation of the study – Safety Set	L3

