At D12 evening	XX (XX.X%)	XX (XX.X%)	XX (XX.X%)
After D12	XX (XX.X%)	XX (XX.X%)	XX (XX.X%)

AXIODIS CRO 40/47

Mock T13

	Healsea Babykids N=XX	Placebo N=XX	Total N=XX
AUC on global score of ARSSQ			
N	XX	XX	XX
Missing	XX	XX	XX
Mean (SD)	XX.X (XX.X)	XX.X(XX.X)	XX.X (XX.X)
Median	XX	XX	XX
Q1/Q3	XX / XX	XX / XX	XX / XX
Min/Max	XX / XX	XX / XX	XX / XX
Between-groups test	XXX (Student/Wilcoxon)		

Mock F2

AXIODIS CRO 41/47

Mock T14

[figure not shown]
	Healsea Babykids N=XX	Placebo N=XX
AUC on global score of ARSSQ		
ANCOVA model :		
AUC = Treatment +		
Type 3 Tests of Fixed Effects		
Treatment	XXX	
	XXX	
Adjusted mean		
LSMeans (SE)	XX.X (XX.X)	XX.X (XX.X)
[LSM 95%CI]	[XX.X; XX.X]	[XX.X; XX.X]
Adjusted mean (diff. vs Placebo)		
LSMeans (SE)	XX.X (XX.X)	
[LSM 95%CI]	[XX.X; XX.X]	
Contrast vs Placebo, p=	XXX	

Mock T15

	Healsea Babykids N=XX	Placebo N=XX
Duration of common cold / cold symptoms / impact of	on Quality-of-Life	
N	XX	XX
Missing	XX	XX
Mean (SD)	XX.X (XX.X)	XX.X (XX.X)
Median	XX	XX
Q1/Q3	XX / XX	XX / XX
Min/Max	XX / XX	XX / XX
Cox survival regression model:		
Hazard Ratios [95%CI]		
Treatment	XX.X [XX.X; XX.X]	
	XX.X [XX.X; XX.X]	
p-values (Wald)		
Treatment	XXX	
	XXX	

AXIODIS CRO 42/47

[figure not shown]
Mock F3

For Treatment: the reference is Placebo

AXIODIS CRO 43/47

Mock F4

AXIODIS CRO 44/47

Mock T16

	Healsea Babykids N=XX	Placebo
Use of XXX	N=XX	N=XX
N	XX	XX
Missing	XX	XX
No	XX.X (XX.X%)	XX.X (XX.X%)
Yes	XX.X (XX.X%)	XX.X (XX.X%)
Logistic model :		,
Odds Ratios [95%CI]		
Treatment	XX.X [XX.X; XX.X]	
	XX.X [XX.X; XX.X]	
p-values (Wald)		
Treatment	XXX	
	XXX	
Number of days of intakes of XXX		
N	XX	XX
Missing	XX	XX
0	XX.X (XX.X%)	XX.X (XX.X%)
1	XX.X (XX.X%)	XX.X (XX.X%)
2	XX.X (XX.X%)	XX.X (XX.X%)
	XX.X (XX.X%)	XX.X (XX.X%)
Poisson regression :		
Type 3 Tests of Fixed Effects		
Treatment	XXX	
	XXX	

AXIODIS CRO 45/47

Mock T17

	Healsea Babykids N=XX		ls Placebo N=XX		Total N=XX	
	n (%)	[E]	n (%)	[E]	n (%)	[E]
Number and percentage of patients with / Number of (non-related)						
Incident (Adverse event)	XX (XX.X%)	XXX	XX (XX.X%)	XXX	XX (XX.X%)	XXX
Incident (Adverse event) leading to definitive study device discontinuation	XX (XX.X%)	XXX	XX (XX.X%)	XXX	XX (XX.X%)	XXX
Incident (Adverse event) leading to definitive study discontinuation	XX (XX.X%)	XXX	XX (XX.X%)	XXX	XX (XX.X%)	XXX
Serious incident (adverse event)	XX (XX.X%)	XXX	XX (XX.X%)	XXX	XX (XX.X%)	XXX
(Treatment-emergent adverse event)	XX (XX.X%)	XXX	XX (XX.X%)	XXX	XX (XX.X%)	XXX

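### The logistic models for medication use have no fallback if an arm has no users in a class (or only users): the odds ratio is then not finite and the Wald p-value tends to 1

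*SAP*

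**What the plan says.** SAP 10.2.3 sets the method: "A multivariate logistic regression model will be used to analyse use (yes/no) of conventional common cold medications". It is applied "overall and by therapeutic class: antibiotics, antipyretics, mucolytics, decongestants, antitussives, systemic and topical corticosteroids". SAP 13.1 lists one table for overall use and one for each of six classes, the last titled "Impact of the treatment on the intake of systemic and topical corticosteroids", so there are seven use models.

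Mock T16 in SAP 13.2 fixes the output. It shows users and non-users by arm as counts and percentages, then "Odds Ratios [95%CI"] for treatment and covariates, then p-values labelled as Wald.

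The covariate rule in SAP 10.2 is: "The selection of variables in multivariate analysis will be performed using a 0.20 significance level and a stepwise method". On software, SAP 6.1 says "The analyses will be computed with SAS Version 9.4 TS Level 1M6" and gives no estimation option. Neither document states a minimum number of users, a penalised or exact form of the model, or what to report when an arm has no users. An exact Fisher test is offered in SAP 8.5, but only for baseline fever.

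**The concern.** Logistic regression estimates a treatment odds ratio only if each arm contains both users and non-users. If one arm has none of either, the likelihood keeps rising as the log odds ratio moves towards infinity. Software stops at an arbitrary point with a huge standard error. The Wald statistic, which divides the estimate by that standard error, shrinks towards zero, so the p-value approaches 1 however many users the other arm has. Baseline covariates do not cure this while treatment stays in the model.

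Reducing the intake of common cold medication is a stated secondary objective. The most favourable result in a class, no users on the device, is one that the planned model cannot summarise. A remedy chosen after unblinding would be post hoc.

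**Working it through.** **Inputs.** Planned arm size 100 (SAP 4: "100 patients by arm are enough to detect" the stated effect); two-sided 5% level (SAP 6.3.1); logistic model with odds ratio, interval and Wald p-value (SAP 10.2.3, Mock T16). Use rates are not in the documents, so a range is assumed.

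**The plan's own figure.** The documents give no calculation for medication use. Their only design figure reproduces: for d=0.4 and 80% power, n = 2(1.960+0.842)²/0.4² = 98.1, so 99 per arm against the stated 100.

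**Step 1: what the model returns for 0/100 v 6/100 users** (treatment-only model, Newton-Raphson).

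| Iteration | Log odds ratio | SE | Wald p |
|---|---|---|---|
| 8 | -6.5 | 10.0 | 0.52 |
| 12 | -10.5 | 73.6 | 0.89 |
| 18 | -16.5 | 1479 | 0.99 |

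The estimate never settles, and the Wald p-value depends on where the program stops.

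**Step 2: methods that stay valid on the same data.**
- Fisher, two-sided: 2·C(100,6)/C(200,6) = 0.029.
- Likelihood ratio: the log-likelihood is 6·ln(0.06)+94·ln(0.94) = -22.697 with separate rates, and 6·ln(0.03)+194·ln(0.97) = -26.948 with a common rate. Twice the difference is 8.50 on 1 df, p=0.0035.
- Firth: odds ratio 0.07, penalised likelihood-ratio p=0.012.

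So the failure lies in the odds ratio, its interval and the Wald p-value, which are the items that Mock T16 prints.

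**Step 3: how often exactly one arm is empty.** With equal true use p and q=(1-p)^100, the probability is 2q(1-q).

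| Use in both arms | Exactly one arm empty | Both empty (q²) |
|---|---|---|
| 1% | 46% | 13% |
| 2% | 23% | 1.8% |
| 3% | 9% | 0.2% |
| 5% | 1.2% | under 0.01% |
| 10% | about 0.01% | under 0.01% |

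The mirror case follows by symmetry. At 95% use, the chance that exactly one arm consists entirely of users is also 1.2%.

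**Step 4: how often a clear difference is affected.** With 0/100 in one arm, Fisher gives p=0.059 against 5 users and 0.029 against 6, so the other arm needs at least 6. The probability is q₁·P(X₂≥6)+q₂·P(X₁≥6), with X binomial on 100. For example, at 1% v 6%: 0.366×0.559 + 0.002×0.0005 = 0.205.

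| True use | Empty arm facing at least 6 users |
|---|---|
| 1% v 1% | 0.04% |
| 2% v 2% | 0.4% |
| 3% v 3% | 0.8% |
| 5% v 5% | 0.5% |
| 1% v 3% | 3% |
| 2% v 5% | 5% |
| 2% v 6% | 7% |
| 1% v 6% | 20% |
| 5% v 10% | 0.6% |

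**The case against.** The strongest reply is that nothing is decided on these p-values. SAP 6.3.1 reserves conclusions for the primary criterion and gives secondary p-values for information only. Mock T16 prints the counts by arm above the model, and SAP 10.3 tabulates concomitant treatments by ATC class and arm, so a 0% v 6% split would be visible. That stands, and it keeps the point minor. It does not make the printed odds ratio and interval interpretable, and a descriptive table should be.

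A second reply is that no document shows any class to be rare; all six are permitted during the study. That also stands. The risk is material only at about 3% use or below and negligible at 10%. Maximum likelihood is itself an inference from the absence of any other named method, although the Wald label is explicit.

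Three stronger readings are tempting, and the documents do not support them.
- A reader might infer that a useful result would often be lost, since at 1% use the chance of at least one empty arm is 60%. But 13 points of that are trials with both arms empty, where no method can compare, and the rate assumes no treatment effect. Step 4 is the relevant measure.
- A reader might infer that overall use fails once nearly every febrile child takes something. The odds ratio becomes non-finite only if every child in an arm is a user.
- A reader might infer that all seven models need replacing. With users and non-users in both arms, this failure does not arise.

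**Conclusion.** The gap is real and small. As written, Mock T16 would print an odds ratio and interval without meaning, and a Wald p-value near 1, for any class in which one arm has no users or only users. Whether that happens depends on use rates that the documents do not give: with 100 per arm and equal use, the chance per class falls from 46% at 1% use to 1.2% at 5%. The chance that it affects a difference significant by Fisher's test is under 1% at equal use. It is about 3% to 20% under the assumed differences of 1% v 3%, 2% v 5%, 2% v 6% and 1% v 6%, but only 0.6% at 5% v 10%. These figures rest on the planned arm size, binomial counts and a treatment-only model. The primary analysis and the sample size are unaffected.

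**What to change.** Add a fallback to SAP 10.2.3 and a footnote to Mock T16, settled before unblinding:

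- When an arm has no users or only users, replace the Wald result by Firth's penalised logistic regression with a profile-likelihood interval and test. Fisher's exact test with an exact or Newcombe interval for the risk difference is an acceptable alternative; name one of the two in advance.
- When both arms have no users, give counts only.
- Label in the table which method was used.

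All other classes keep the planned model. The cost is one extra model option and a table footnote. Firth shrinks the odds ratio somewhat, and the Fisher alternative is unadjusted, so these rows are not strictly comparable with the others.

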7.3.1 Eligibility Criteria

7.3.1.1 Inclusion Criteria

Subjects will be enrolled if they meet all of the following criteria:

- 1. Male/Female subjects >2 and ≤6-year-old
- 2. Acute infectious rhinitis/rhinosinusitis for ≤48h before trial entry
- 3. Patient presenting with fever ≥ 37.5 °C at screening
- 4. Subjects with nasal congestion (blocked / stuffy nose) rated at least as moderate on the Acute Rhinitis Symptoms Severity Questionnaire, based on evaluation by the investigator
- 5. Subjects showing at least moderate grade for at least one of the following additional signs of acute rhinitis: runny nose, nasal crust (dry mucus), sneezing and cough
- 6. Written consent obtained from parent/legal guardians

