8.4 Secondary endpoints

A Cox survival regression model will be used to analyse the secondary endpoints of **duration of cold symptoms and of impact on quality of life**.

A multivariate Poisson regression model will be used to analyse the secondary endpoint related to the **number of days of use of conventional common cold medications** (overall and by therapeutic class).

A multivariate logistic regression model will be used to analyse the secondary endpoint related to the use (yes/no) of conventional common cold medications (overall and by therapeutic class).

-Safety: Adverse events/ incidents will be summarized by the number of occurrences, the number and percentage of patients by treatment group, classified by System Organ Class and Preferred Term as defined by MedDRA dictionary. Only treatment-emergent events will be analysed.

Frequency and percentage of patients with at least one reported adverse event/ incident / expected side effects will be tabulated by System Organ Class and by treatment group.

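### Days of cold-medication use are analysed by Poisson regression with no allowance for overdispersion, so p-values would be too small in classes that a minority of children take in multi-day courses

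*SAP*

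**What the plan says.** For days of use, SAP 10.2.3 states: "A multivariate Poisson regression model will be used to analyse the number of days of use of conventional common cold medications". The classes are listed with the companion yes/no logistic model: "overall and by therapeutic class: antibiotics, antipyretics, mucolytics, decongestants, antitussives, systemic and topical corticosteroids". Six classes plus the overall count make seven Poisson models. Protocol 8.4 specifies the same approach: "A multivariate Poisson regression model will be used to analyse the secondary endpoint related to the" days-of-use count.

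The outcome is a sum within each child: "The total number is the sum of all distinct days of use of these medications, from D1 to D18". It can therefore run from 0 to 18.

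SAP 10.2 applies stepwise selection at the 0.20 level. "Covariates considered as potential confounding factors to be initially tested with the treatment in the multivariate models are" body temperature and ARSSQ items 2 to 7, seven in all.

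For the logistic model, Mock T16 shows odds ratios with 95% CIs. For days of use it shows the distribution of days by arm, and then for the Poisson model only "Type 3 Tests of Fixed Effects". There is no rate ratio, interval or dispersion estimate.

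SAP 6.3.1 limits the status of these results: "P-values of statistical tests on secondary criteria will be provided for information only".

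**The concern.** Poisson regression takes its standard errors from the assumption that variance equals mean. A days-of-use count meets this only by accident. A child who never uses a class contributes 0, and a child given a course contributes several days at once. If users are a minority and courses last several days, the counts vary far more than their mean. The model then understates the standard error of the treatment effect and prints a p-value that is too small.

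At stake is the secondary objective on medication intake. Antibiotics and corticosteroids are plausible low-use, multi-day classes, and there a chance imbalance of a few courses between arms could look like a medication-sparing effect. With no rate ratio or interval from the model, nothing printed beside the p-value would show how imprecise the comparison is.

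**Working it through.** **Inputs from the documents.** The arm size is 100, with 1:1 allocation (SAP 4), and the test is two-sided at 0.05 (SAP 6.3.1). The documents give no figure for the Poisson analysis. Their sample-size statement for the primary endpoint reproduces: an effect size of 0.4 with 80% power needs 99 per arm, and 100 per arm gives about 80% power. It is used here only for the arm size.

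**Inputs that are assumptions.** The share of users p and the course length are not given for any class, so a range is shown. Course lengths are taken as 1 + Poisson(L − 1), with mean L and variance L − 1, capped at 18 days.

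**Formulae.** Let a child be a user with probability p and take a course of mean m and variance s². The mean count is pm and the variance is ps² + p(1 − p)m². Hence

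φ = variance / mean = s²/m + (1 − p)m, which is (L − 1)/L + (1 − p)L for these course lengths.

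Under no treatment effect, the nominal 5% Poisson test rejects with probability about 2[1 − Φ(1.96/√φ)].

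**Worked example.** For 20% users and 5-day courses, φ = 4/5 + 0.8 × 5 = 4.8. Then 1.96/√4.8 = 0.895, and 2[1 − Φ(0.895)] = 0.371.

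**Results.** The simulated column is the likelihood-ratio test in a treatment-only model, with 20,000 null trials per pattern.

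| Users | Mean days | φ | Formula | Simulated |
|---|---|---|---|---|
| 10% | 7 | 7.16 | 46.4% | 47% |
| 20% | 7 | 6.46 | 44.1% | 44% |
| 20% | 5 | 4.80 | 37.1% | 38% |
| 40% | 5 | 3.80 | 31.5% | 32% |
| 60% | 5 | 2.80 | 24.1% | 24% |
| 85% | 5 | 1.55 | 11.5% | 11% |
| 95% | 5 | 1.05 | 5.6% | 5.5% |
| 95% | 3 | 0.82 | 3.0% | 3.0% |
| 100% | 5 | 0.80 | 2.8% | 2.9% |

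Repeat simulations agree within about one percentage point.

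**Where the problem stops.** Setting φ = 1 gives p = 1 − 1/L², that is 89%, 96% and 98% users for 3-, 5- and 7-day courses. If all courses are equally long it gives p = 1 − 1/L, that is 67%, 80% and 86%. Above these shares the Poisson p-value is too large instead of too small. This is possible for antipyretics and the overall count, because protocol 7.3.1.1 requires "Patient presenting with fever" at screening.

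**Other course lengths.** With lengths spread evenly over a range, simulated rejection rates are:
- 10% users, 5 to 7 days: 41.0%
- 20% users, 3 to 5 days: 29.0%
- 40% users, 1 to 3 days: 11.3%
- 90% users, 5 to 7 days: 2.0%
- single-day use by 10% to 50% of children: 4.1% falling to 0.5%

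**Covariate adjustment.** Seven baseline covariates were all kept in the model, with 3,000 null trials per pattern. For the first five rows of the table the rates are 46%, 44%, 36%, 29% and 24% with moderately prognostic covariates, and 46%, 41%, 34%, 27% and 21% with strongly prognostic ones. A smaller check used backward selection at 0.20 as a stand-in for stepwise, with 400 trials per scenario and a standard error of about 2 to 2.5 points. It gave 34.5% (10% users, 5 to 7 days), 33.8% (20%, 5 to 7 days), 22.0% (30%, 3 to 5 days) and 13.8% (20%, 1 to 3 days).

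**Reading a printed p-value.** At φ = 4 the test statistic is inflated twofold. A printed 0.05 corresponds to 2[1 − Φ(1.96/2)] = 0.33, and a printed 0.01 to about 0.20.

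**After correction.** Robust variance gives 4.1% to 5.3% in the treatment-only model for 10% to 100% users, and 4.2% to 6.2% in the adjusted models. Pearson scaling gives 3.6% to 8.1% in the adjusted models.

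**The case against.** The strongest objection is about weight. SAP 6.3.1 treats everything except the primary criterion as descriptive, so the type I error of these tests is the error of tests on which no conclusion rests. That limits the harm but does not remove it: a p-value offered for information should still be right. Medication intake is a stated secondary objective, protocol 7.1.4 predicts a reduction in rescue medication, and SAP 10.2.2 itself reads a secondary log-rank p-value against 5%.

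Second, Mock T16 is not empty. Its rows for 0, 1, 2 and more days by arm let a careful reader work out mean days, a crude rate ratio and the dispersion, and the logistic part gives an odds ratio with its CI. This stands. What is missing is a model-based rate ratio with a valid interval.

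Third, no class can be shown to be affected, because usage is unknown, and the absence of a correction is inferred from silence. Both are true. But an unstated program option is not pre-specified, and robust variance does not require a guess about which classes are overdispersed.

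Fourth, the correction is imperfect in very rare classes. With 2% to 5% users and 7-day courses, robust variance rejects in only about 1.0% to 3.4% of null trials. An arm has no users in about 1% of trials at 5% use, 9% at 3% and 25% at 2%, and then no log rate ratio can be estimated. This also stands and shapes the fix. Plain Poisson rejects in 48% to 53% of trials in the same patterns, so the correction is still a clear improvement.

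**Conclusion.** The concern holds, conditionally. Wherever a class is used by a minority of children in multi-day courses, the model as written gives p-values that are too small. With 10% to 40% users and mean courses of 5 to 7 days, the nominal 5% test rejects a true null in roughly 32% to 47% of trials in the treatment-only model. Covariate adjustment leaves the problem largely in place. The claim does not extend to all seven models: with near-universal or single-day use the test is about right or conservative.

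The sizes rest on assumed user shares and course lengths; the direction follows from the variance formula. The primary conclusion, the sample size and the yes/no logistic analysis are unaffected. It is a cheap improvement to a secondary analysis that is worth making.

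**What to change.** In SAP 10.2.3, state that days of use, overall and by class, will be analysed by Poisson regression with robust (sandwich) variance. In Mock T16, add the rate ratio versus Placebo with its 95% CI beside the p-value.

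Negative binomial regression for overdispersed counts, or Pearson-scaled variance, is an acceptable alternative where a class has enough users. Robust variance should lead, because Pearson scaling reached 8.1% in the adjusted checks and 17.5% at 2% users. It would also help to say that only the counts by arm will be shown for a class with no users in one arm.

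The cost is a line or two in SAP 10.2.3, one option in the SAS call and one row in Mock T16. The SAP is marked final, but protocol 8.10 already provides for reporting deviations from it. The downside is less favourable p-values in overdispersed classes. Where nearly every child is a user, little changes.
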